### 4.3 Study Enrollment Procedures

The clinical treatment site will maintain a screening and enrollment log to track screen failures and enrollment (See Appendix A). A subject will not be screened until an Informed Consent Form has been signed. A subject's reason for ineligibility and reasons for nonparticipation or withdrawal from the study will be documented for inclusion in the Trial Master File (TMF).

Subjects who appear to meet the criteria for study participation will be informed of the study and, if interested, will review the study consent(s) with a qualified individual (approved by the PI to administer consent and listed on the Delegation of Authority Log).

During the informed consent process, study staff will detail the study procedures to ensure that the subject understands the study procedures and what is involved prior to signing the informed consent document. Subjects will be informed that they can withdraw from the study at any time and receive alternative care outside of the study. Subjects will be afforded as much time as needed to make an informed decision regarding willingness to participate in the study. Additionally, the study staff will provide contact information and will be available to discuss any questions or concerns potential subjects may have.

At the time of enrollment, immediately after written informed consent is obtained and before performing any study-related procedures, each subject will be assigned a unique sequential subject number for identification throughout the study by the study staff. This subject number will not be reused for any other participant in the study.

Once a subject has successfully met all inclusion and exclusion criteria, the subject will be randomized using the random number generator in a 1:1 ratio to EVPOME or POM via the web-based Treatment Assignment Tool U-M (TATUM) to obtain the subject's treatment assignment. The randomization schedule will begin with block sizes of 2, 4, or 6.

Upon randomization, an email will be sent to the Co-Investigator and/or any appropriate study staff. Randomization numbers will be assigned in the order in which subjects qualify for treatment, not in the order of study enrollment.

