#### 5.4 Adherence Assessment

During each post-surgery visit, study subjects will be questioned on adherence to post-operative guidelines including dental hygiene, alcohol consumption, and smoking abstinence to assess correlation of these factors with graft contracture and revascularization.

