#### 6.2.3 **Visit 3: Baseline: Intraoral Grafting of EVPOME or POM Grafts**

Grafts will be applied as determined by the randomization schedule. Group 1 subjects will undergo intraoral grafting of EVPOME and Group 2 subjects will receive POM that will be harvested at this time from the donor site, palate. For Group 1 subjects, before release of the EVPOME for grafting from the CTML, glucose utilization will be measured and determined as percent of glucose utilized by the EVPOME during the final days of laboratory incubation. Gram stain analysis will be performed on culture media that the EVPOME was grown in during the final day of incubation. Preliminary results of in-process sampling to determine the sterility (aerobic, anaerobic, and fungal cultures) of the product will

3/28/2017

be reviewed. Results of in-process mycoplasma testing will be reviewed. Analysis of in-process sampling for endotoxin will also be reviewed. If the device fabrication is unsuccessful, the subject will be given the opportunity to have a second palatal or retromandibular trigone (location is at the discretion of the principal investigator and the surgeon) biopsy taken for production of another EVPOME device.

Every effort will be made to maintain contact with the subject for safety data should the subject decline a second biopsy and withdraw from the study to pursue standard of care treatment. It is important to note that in our completed Phase I clinical trial we did not have to abort any procedure because of in-processing difficulties in not achieving our release criteria of passing the sterility tests and satisfying glucose consumption over the last 24 hours. Samples of spent media that the EVPOME was grown in may be stored and analyzed for proteins or other cell secretions in order to better understand graft success or failure.

EVPOME and POM grafts will be sutured and assessed to assure they are immobile. Subjects will be given standard post-operative instructions which may include analgesics and antibiotics per standard of care.

Intraoral photographs will also be taken at this time. A maxillary stent will be placed at this time for the POM subjects.

A visual analog scale of pain will be taken at this time for both group I and II and subjects will also be questioned about any adverse events.

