### 9.3 Sample Size and Accrual

We propose to have 60 subjects to give clinical and histological endpoints of interest at the primary assessment time of 4 weeks post graft. We expect no more than 6 subjects to potentially drop out of the study before providing Week 4 data, and thus will enroll 66 patients in total. With an estimated enrollment of 1 out of 5 screened patients, we expect to have a pool of over 330 patients over two years from which to select 66 subjects (33 subjects per group over two years) that will be randomized equally to one of the two groups - EVPOME and POM grafts. The randomization list will be prepared electronically in advance by the biostatistician and transferred to the MICHR statistics group for incorporation into the TATUM system. Randomization will be stratified by smoking status.

The primary clinical endpoint is the degrees of keratinized tissue. Secondary outcomes are contracture and wound healing index. Ancillary endpoints include the presence or absence of a continuous epithelial layer, the degree of vascular ingrowth, the LDF measurement of gingival blood flow. The main aim is to show that EVPOME treatment give comparable clinical and histological results when compared with POM treatment. It is also expected that the EVPOME will cause less patient discomfort and pain, and have a better color rendition to the surrounding tissue than the POM. Hence, we expect EVPOME to show better outcomes for pain, color rendition, and microvessel infiltration than POM, while showing comparable outcomes on primary endpoints of keratinized tissue and graft contracture or histological endpoints compared with POM. Sample size is calculated to show near equivalence of the two groups for primary and secondary outcomes. Sample size calculation and power consideration are provided following the data analytic plan described for each outcome.

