**Laser Doppler Flow (LDF):** LDF data will be compared based on gingival blood flow at Week 4 post-surgery at the graft site between the EVPOME and POM groups. One aspect of this study will be to examine and explore the usefulness of this measure. In particular, we will explore the use of control measures taken on normal tissue to help adjust for intra subject factors contributing to the variability. The primary investigation will compare gingival blood flow at the graft site at two weeks, four weeks, eight weeks, and 24 weeks post-surgery to the values in an analysis of covariance (ANCOVA) model. The corresponding differences at the control site will also be incorporated as a covariate to partially adjust for intra-individual variability. More detailed analyses will utilize ANCOVA methods for repeated measures. There is relatively little background data on the use of LDF to measure perfusion in the context being studied here though some preliminary data on measuring gingival blood flow can be found in Justus et al. where change in gingival blood flow from baseline to post surgery (over the period 7 to 24 .days) was found to have a mean of about -25 perfusion units (PU) with an SD of about 60 PU. The measurement is highly variable.

For repeatedly measured data such as pain and wound healing index, data will be

summarized by treatment groups at each follow-up time. In addition, linear mixed-effects models will be used to make the between group comparison while adjusting for potential within person correlation of the outcome variables. By using the modeling approach, it will be possible to incorporate all observations from both treatment groups and make between treatment group comparisons efficiently using a treatment dummy indicator. The model will allow us to not only compare the time-averaged means, but also allows us to explore the rate of decline between the EVPOME and POM groups such as the rate of decline in pain, using appropriate interactions terms. When appropriate, comparisons between treatments will be adjusted for surface area of the graft as well as measures of its geometry, and other variables including age, general health and alcohol use.

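### The planned adjustment list includes graft size and alcohol use, which as scheduled are recorded after randomization, and omits the baseline outcome value and the stratification factor

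*Combined protocol and SAP*

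**What the plan says.** The last sentence of section 9.5 closes the paragraph on linear mixed models for repeated measures such as pain and the Wound Healing Index. It makes adjustment conditional on being appropriate and states: "comparisons between treatments will be adjusted for surface area of the graft as well as measures of its geometry". Its list also names age, general health and alcohol use, and is left open. It does not say which graft size is meant, when alcohol use is recorded, or who judges when adjustment is appropriate.

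Other sections fix the timing:

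- **Randomization.** Section 4.3: "Once a subject has successfully met all inclusion and exclusion criteria, the subject will be randomized". The schedule in 6.1 puts this at Visit 1.
- **Graft.** Section 6.2.3, Visit 3 (Day 0): "Grafts will be applied as determined by the randomization schedule".
- **Alcohol.** Section 5.4, at each post-surgery visit: "study subjects will be questioned on adherence to post-operative guidelines including dental hygiene, alcohol consumption, and smoking abstinence". Section 5.3.2 prohibits alcohol during the study. At screening the only alcohol item is the exclusion for a history of abuse in 4.2.
- **Stratification.** Section 9.3: "Randomization will be stratified by smoking status".

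Under Aims 1 and 2 of section 9.5, the Week 4 KM and contracture comparisons are each an equivalence test of means, with no covariates named.

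**The concern.** Randomization protects a treatment comparison adjusted for characteristics fixed before allocation. It does not protect one adjusted for something that allocation, or the course after it, may have changed. Two of the listed items fall in the second group as the plan records them.

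The placed graft is cut and sutured after allocation, by surgeons who know the arm. Alcohol use at follow-up visits is a measure of adherence and could respond to pain. Pain is one of the outcomes that the mixed models compare, and section 9.1 includes superiority on pain in the primary hypothesis. If drinking responds to pain, adjusting the pain comparison for it can distort that result.

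The covariates with the strongest claim to inclusion are missing: the baseline value of the outcome, and the factor used to stratify randomization. The open wording also lets both the decision to adjust and the choice of variables be made after the data are seen.

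**Working it through.** **1. Timing of each covariate**

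| Covariate | Named in 9.5? | When fixed or recorded |
|---|---|---|
| Age, general health | Yes | Before randomization (6.2.1) |
| Graft area and geometry | Yes | Placed graft: Visit 3. Planned size: could be set at eligibility (4.1.5) |
| Alcohol use | Yes | Scheduled only after surgery (5.4) |
| Smoking stratum | No | Before randomization (9.3) |
| Screening pain VAS | No | Visit 1, both groups (6.1, 6.2.1) |
| Screening KM width | No | Visit 1 under clinic assessments (6.1), but 6.3.5 lists only visits 5 to 8 |

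Contracture is 100 × (1 − final area / Day 0 area). If a follow-up area were used to adjust contracture, the model would condition on part of its own outcome.

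**2. The plan's own figure for KM**

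Inputs from 9.5, Aim 1: SD 0.65 mm, 30 per arm, true difference 0, margin 0.55 mm, two-sided 95% confidence interval.

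- SE = 0.65 × √(2/30) = 0.168 mm (plan: 0.17).
- Margin of error = 1.96 × 0.168 = 0.329 mm (plan: about 0.33).
- Power = 2Φ(0.55/0.168 − 1.96) − 1 = 2Φ(1.317) − 1 = 81.2% (plan: at least 80%).

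The plan's figures reproduce. With a t critical value on 58 degrees of freedom and an estimated SD, power is about 79%.

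**3. Power with pre-randomization covariates**

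The documents give no correlation between baseline and Week 4 KM width. I assume 0.3 to 0.5 and also show zero.

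- Adjusted SD = 0.65 × √(1 − ρ²): 0.620 mm at ρ = 0.3, 0.563 mm at ρ = 0.5.
- Residual degrees of freedom = 58 − k for k covariate degrees of freedom.
- Chance imbalance in the covariates inflates the variance on average by 57/(57 − k): 1.018 for k = 1, 1.036 for k = 2, 1.096 for k = 5.

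Simulated power, with one covariate carrying the whole correlation and the others explaining nothing:

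| Covariate df | ρ = 0 | ρ = 0.3 | ρ = 0.5 |
|---|---|---|---|
| 0 | 79.3% | – | – |
| 1 | 78.3% | 83.5% | 91.6% |
| 2 | 77.1% | 82.5% | 90.9% |
| 5 | 73.4% | 79.2% | 88.7% |

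At ρ = 0.3 and k = 5 the SE is about 0.160 × √1.096 = 0.168 mm, the same as unadjusted. A long list cancels the gain.

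**4. Bias from a post-randomization covariate**

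Shift in the estimate = outcome slope on the covariate × arm difference in the covariate. In SD units this is r × d. The documents give neither r nor d, so the following only shows how the formula behaves. With r = 0.3 to 0.5 and d = 0.25 to 0.8, the shift runs from 0.3 × 0.25 = 0.075 SD to 0.5 × 0.8 = 0.40 SD. If the sentence reached KM width, that would be 0.05 to 0.26 mm, or 9% to 47% of the 0.55 mm margin.

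**The case against.** The case for the plan is substantial, and much of it stands.

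- **The primary test may be untouched.** The adjustment is conditional and sits in the repeated-measures paragraph. A reader might infer that the primary KM comparison is biased. The documents do not show this, because Aims 1 and 2 describe unadjusted tests. What remains is doubt about scope, since the sentence speaks of treatment comparisons without limiting them.
- **Graft size may not differ by arm.** A reader might infer that palatal grafts are limited by the donor site while manufactured grafts are not. No section says so. Section 6.3.2 sets one standard trapezoid, up to the same dimensions, for both arms, and 5.1.6 speaks of a standardized size. Actual size may still vary below that limit.
- **Planned size is legitimate.** Graft need is an eligibility item (4.1.5). If 9.5 means a size planned before randomization, adjusting for it is sound. The plan does not say.
- **Alcohol timing is inferred.** Section 9.5 does not date it. Medical history is taken at Visit 1 and could include it, and the prohibition in both arms may leave little variation. Still, 5.4 is the only scheduled collection.
- **Some baseline covariates are named.** Age and general health are in the sentence, so it would be wrong to say that the plan ignores pre-randomization predictors.
- **The precision gain is not assured.** Eligibility restricts baseline KM to 3 mm or less and it is read to the nearest millimeter, both of which tend to lower the correlation.

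**Conclusion.** The point holds in a limited form. As scheduled, placed graft size and alcohol use are recorded after randomization, and adjusting for them can bias the mixed-model comparisons, pain included. The direction and size of that bias cannot be derived from the documents. The baseline outcome and the stratification factor are unnamed, and the scope and content of the adjustment are open. Whether the Week 4 KM and contracture tests are affected is unclear; the text does not establish that they are.

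The precision argument is secondary and rests on an assumed correlation of 0.3 to 0.5. Under it, one baseline covariate raises KM power from about 79% to about 84–92%, and two to about 82–91%. A reader using the normal approximation might infer 86–93%. That ignores the t critical value and chance imbalance, and does not hold for a five-degree-of-freedom list, which gives about 79–89%. If the correlation is near zero, adjustment costs a little power: about 78% with one covariate.

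**What to change.** Replace the sentence in 9.5 with a short, fixed list of pre-randomization covariates for each outcome, and delete the open conditions.

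- **Week 4 KM:** ANCOVA with screening KM width and smoking stratum.
- **Pain:** mixed model with screening VAS and smoking stratum.
- **Contracture and Wound Healing Index:** smoking stratum, as neither has a pre-surgery value.
- **Age:** optional; decide in advance.
- **Graft size:** only as planned before randomization, and recorded then.
- **Alcohol use:** only if recorded at screening.

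Otherwise keep graft size and alcohol use for correlation analyses such as those in 5.4.

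Two supporting corrections are needed. State what the smoking strata are, since the population is non-smoking; former versus never smokers would fit 4.2, but this is not stated. Confirm that KM width is measured at Visit 1, since 6.1 and 6.3.5 differ. An outcome defined as an increase needs that value in any case.

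The cost is SAP wording and, for KM, two of 58 degrees of freedom. No added subjects are needed. The downside is slightly lower power if the baseline correlation is near zero (about 77% with two covariates).

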## 10. DATA COLLECTION, SITE MONITORING, AND ADVERSE EXPERIENCE REPORTING

### 10.1 Records to Be Kept/Case Report Forms

Data for this study will include subject source data for all clinical data assessments as described in the protocol and subject safety and efficacy data.

- Data will be stored in the study database and will be password protected. All research staff requiring access will be assigned a unique login name and password.
- Data for subjects, including documentation of informed consent, will be stored in a locked area accessible only by study research personnel.

The research team will develop paper Case Report Forms based on data collection requirements outlined in the protocol. These paper forms will serve as back-up to the electronic data entry screens that are created during development of the project database. The site coordinator will be responsible for completing paper forms and entering the results into the data management system. Alternatively, results may be entered directly into the project database via the data management system's web-based interface. The data collection instruments will undergo internal quality checks, and review and acceptance testing prior to their release for use. Paper Case Report Forms will be maintained at the study site and stored in compliance with Good Clinical Practice and relevant institutional policies.

Once completed, the study data will be archived in a secure location and documented by the Study Investigator. An Electronic Trial Master File (TMF) will be retained. All expected research data must be entered into the data management system and any data discrepancies resolved before the database is locked. Edit access to the study database will be restricted to read-only at this time. A read-only, time-stamped snapshot of the data will be created for analysis. Following data analysis, the database is frozen and access rights to the database are revoked. Only approved changes that significantly affect data

3/28/2017

analysis are permitted once the database has been frozen. A snapshot of the frozen database is archived. Both the lock and freeze snapshots will be transmitted to the study team as password-protected files or via MiShare, a secure file transfer system supported by Medical Center Information Technology (MCIT).

## 10.2 Role of Data Management

The data management group will create a validated, 21CFR part 11 compliant database using the OpenClinica system. To ensure quality data, logic checks will be incorporated into the database. Discrepancy management will also be performed both manually and through the use of programmed validation checks within the system to ensure high quality data. Data extracts in the form of tables and reports will be exported from the database routinely to assess study progress, enrollment, safety, and efficacy. These reports are made available to the Investigator and the Statistician, as needed.

## 10.3 Quality Assurance

To ensure the highest level of data integrity and quality assurance, the study will be monitored by a qualified clinical trial monitor.

The purpose of monitoring is to ensure that the rights and safety of the participants are protected and the study is implemented in accordance with the protocol, Good Clinical Practice, applicable federal and local regulations, and the quality and integrity of the study data are maintained.

The clinical site monitoring plan will specify the frequency, procedures, levels of monitoring activities, and a monitoring communication plan. Monitoring activities will include the site initiation (pre-investigation) visit, interim site monitoring visits, and a close-out visit. The plan may also include for-cause visits. During the interim monitoring visits, the monitor will review participant medical and research records, consent documents, unanticipated problems, serious adverse events, site regulatory documents, etc. A summary of findings will be documented in a monitoring report and action items will be reviewed and followed until closed. Complete monitoring visit documentation will be provided to the study PI/Site PI and sponsor.

A site initiation visit will be scheduled prior to site activation and enrollment, and interim site visits will occur at least annually.

The sponsor or other regulatory officials may perform an audit or may accompany the clinical monitor on a monitoring visit.

The Medical Monitor, [name], will be available to review significant protocol deviations and AEs/SAEs on a scheduled and as needed basis.

## 10.4 Adverse Experience Reporting

Adverse Events (AEs) other than routine, mild and expected experiences, either observed by the Investigator or one of his/her medical collaborators, or reported by the subject, will be documented. These AEs will be followed until the event is resolved, until the event is deemed chronic, or until 30 days after the subject's participation in the study has ended.

Expected, routine, mild adverse experiences include: lack of sensation, numbness, swelling, bleeding, and pain associated with the grafting site and lack of adherence of the graft. These adverse experiences will be documented in the medical record.

Any Serious Adverse Event (SAE) that occurs must be reported to the University of Michigan IRB (IRBMED) according to the IRBMED reporting guidelines. Information about all SAEs is collected and recorded on the Serious Adverse Event Report Form. All pertinent medical records and information collected during the treatment and follow-up of the subject should be maintained. The Investigator must assess the SAE relationship to investigational product. All SAEs will be reported to the FDA in compliance with the FDA reporting requirements as found under 21 CFR 312.32. This includes reporting to the FDA all unexpected, fatal or life-threatening adverse events assessed as related to the product by telephone or fax within seven days and the reporting in writing of unexpected serious adverse events assessed as related to the product within 15 days.

Expected Serious Adverse Events include allergic reaction, uncontrollable bleeding and/or pain or an infection requiring hospitalization.

Any death occurring through the end of the study (30 days following the intervention), regardless of the degree of relationship to study, must be reported as a Serious Adverse Event.

The investigator will submit an attribution for the relatedness of the adverse event to the test article or procedure. As far as possible, each AE should be evaluated to determine:

- the severity grade (mild, moderate, severe);
- its relationship to the study investigational product(s);
- its duration (start and end dates or, if ongoing, at final exam);
- action taken; and
- seriousness (yes/no)

The severity grade should be determined by the Investigator using the definitions below:

- Mild: Discomfort noticed but no disruption of normal daily activity;
- Moderate: Discomfort sufficient to reduce or affect normal daily activity; or
- Severe: Inability to work or perform daily activity.

The relationship of AEs to the investigational product should be determined by the Investigator using the definitions below:

- Definitely related: clearly associated with study drug/treatment;
- Probably related: likely associated with study drug/treatment;
- Possibly related: may be associated with study drug or other treatment;
- Unlikely to be related; or
- Definitely not related to the study drug/treatment.

For reporting purposes, an AE should be regarded as definitely or probably related to the regimen if the investigator believes that at least one of the following criteria are met:

- a. There is a clinically plausible time sequence between onset of the AE and the administration of the study drug or treatment;
- b. There is a biologically plausible mechanism for the study drug or treatment causing or contributing to the AE;
- c. The AE cannot be attributed solely to concurrent/underlying illness, other drugs, or procedures; or
- d. A potential alternative cause does not exist.

Expected adverse events are those adverse events that are listed in the study informed consent documents.

Unexpected adverse events are those that are not described in the study informed consent. This includes adverse events for which the specificity or severity is not consistent with the description in the informed consent.

Should an unanticipated problem occur during the investigation, the investigator will report them to IRBMED, the FDA, and DOD according to the reporting requirements of each entity.

An unanticipated problem is any incident, experience, or outcome that meets ALL three of the following conditions:

1. Is unexpected (in terms of nature, severity, or frequency) given the procedures described in the research protocol documents (e.g., the IRB-approved research protocol and informed consent document) and the characteristics of the human subject population being studied;
2. Is related or possibly related to participation in the research (possibly related means there is a reasonable possibility that the incident, experience, or outcome may have been caused by the procedures involved in the research); and
3. Suggests that the research places human subjects or others at a greater risk of harm (including physical, psychological, economic, or social harm) than was previously known or recognized, even if no harm has actually occurred.

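### Section 10.4 contradicts itself on relatedness: plausible timing alone earns a reporting label that its own five-level scale keeps for clear or likely association

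*Combined protocol and SAP*

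**What the plan says.** Section 10.4 (Adverse Experience Reporting) contains two rules on relatedness, one directly after the other.

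- **The scale.** The investigator grades each AE by verbal definitions: definitely, probably, possibly, unlikely, or definitely not related. Definitely requires a clear association and probably a likely one. The middle grade reads "Possibly related: may be associated with study drug or other treatment".
- **The reporting rule.** The next sentence is limited to reporting and regards an AE as "definitely or probably related to the regimen if the investigator believes that at least one of the following criteria are met". Criterion (a) concerns timing and reads "There is a clinically plausible time sequence between onset of the AE and the administration of the study drug or treatment". Criterion (b) asks for a credible biological route from treatment to event. Criterion (c) is met when other illness, drugs or procedures do not wholly explain the event; it closes with an or, which makes the list disjunctive. Criterion (d), the strictest, reads "A potential alternative cause does not exist".

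Earlier in 10.4, relatedness is one condition for expedited FDA reports: within seven days for unexpected fatal or life-threatening events, and in writing for "unexpected serious adverse events assessed as related to the product within 15 days". Later in 10.4, the definition of an unanticipated problem accepts events that are related or possibly related, and explains possibly as a reasonable possibility of causation. The section does not say how the a-d rule maps onto the five grades, or which of the two rules defines related for the FDA reports.

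**The concern.** The two rules can give the same event different grades. A plausible time sequence is weaker evidence than a clear or likely association, yet under the reporting rule it is enough for the top label. Both arms have surgery on Day 0, so many unrelated post-operative AEs could meet criterion (a).

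Three things are at stake: the specificity of expedited FDA reports, the meaning of any table of related AEs, and consistency between investigators. Safety is part of the primary objective (Section 1.1), so the attribution label should separate likely from merely conceivable causation.

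**Working it through.** No power, alpha or sample-size figure is involved, and the plan gives no figure to reproduce. The check is an enumeration of the rule.

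**Inputs (all Section 10.4).** Four yes/no criteria a-d; at least one needed; result if met: definitely or probably related.

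**Step 1: all patterns.** Four binary criteria give 2^4 = 16 patterns. Only the pattern with none met escapes the rule, so 16 - 1 = 15 lead to the top label.

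**Step 2: coherent patterns.** If no alternative cause exists (d), the event cannot be attributed solely to another cause (c), so d implies c. Patterns with d met and c not met are impossible. There are 2 x 2 = 4 of these (a and b free), which leaves 16 - 4 = 12 coherent patterns. Of these, 12 - 1 = 11 lead to the top label. Because d implies c, criterion d adds nothing when any one criterion is enough.

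**Step 3: what is left.** The remaining pattern has no plausible timing, no plausible mechanism, possible sole attribution to another cause, and an existing alternative. That describes unlikely or definitely not related. An event that may be associated with treatment would ordinarily have at least plausible timing or a plausible mechanism, and so would already have been moved up. For reporting, nothing workable remains for the middle grade.

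**Step 4: the rules side by side.** Take an event with plausible timing and an obvious other cause, such as a sore throat on Day 5 after a known viral contact.

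- *Scale:* neither clearly nor likely associated.
- *Unanticipated-problem definition:* can fail even the reasonable-possibility test.
- *a-d rule:* meets (a), so definitely or probably related.

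The top label can therefore be easier to reach than the middle one.

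**Step 5: size in events.** Among truly unrelated AEs, the share given the top label is at least the share with plausible timing. The documents give no figure for that share. If it were 50% to 90% (assumption), at least 50% to 90% of unrelated AEs would carry the label. Steps 1 to 4 do not depend on this range.

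**Step 6: where the label matters.** It bears on the 7- and 15-day FDA reports and on any table of related AEs. Section 10.4 requires deaths through the end of the study to be reported whatever their attribution, and sets no attribution filter on reporting SAEs to the IRB. The DSMB reviews SAEs (Sections 10.5 and 13), and the triggers in Section 13 count events in 5 experimental subjects without an attribution filter. Section 9.5 plans no analysis of related AEs.

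**The case against.** The strongest defence is that the a-d rule is limited to reporting, while the recorded grade comes from the verbal definitions. An investigator could record possibly related and still apply the broader rule when deciding what to report. A wide net is also the cautious choice for a phase II cell product. Expedited reports require the event to be unexpected and serious as well, so the sore throat, if non-serious, would trigger none. Section 7 already keeps mild, routine post-operative experiences out of the AE count unless they exceed what is expected.

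Most of this stands, and it rules out several stronger readings that a reader might infer:

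- *That possibly related can never be recorded.* The text does not say that the reporting rule overwrites the recorded grade. The two rules are simply unreconciled.
- *That all four criteria are weak.* Criterion (d) is strong. The breadth comes from needing only one.
- *That related-event counts carry no information, or equal all-AE counts.* Events that fail all four criteria are still separated.
- *That a planned comparison with POM is spoiled.* None is planned.
- *That nearly every post-operative AE will be labelled related.* No figure in the documents supports this, and criterion (a) calls for the investigator's judgement, not merely onset after grafting.

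The defence does not remove the contradiction. Expedited reporting is where relatedness has a stated consequence. There, the text allows three readings of related: the top two grades of the scale, possibly and above, or the a-d rule. A preference for wide reporting does not require calling such events definitely or probably related.

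**Conclusion.** The contradiction is real and can be seen from the text of Section 10.4 alone. For reporting, 11 of 12 coherent criterion patterns lead to definitely or probably related, plausible timing is sufficient by itself, and the middle grade has no workable content. The top grades would be inflated and poorly specific, and the meaning of related for the 7- and 15-day FDA reports is left open.

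The reach is limited. The rule errs toward over-reporting and does not touch the planned efficacy analyses, the handling of SAEs and deaths, DSMB review or the stopping triggers. The pattern counts rest only on reading the list as disjunctive, which its wording makes explicit, and on d implying c. They are counts of logical patterns, not of expected events. This should be corrected, but it does not threaten the trial's conclusions.

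**What to change.** 1. Keep the five verbal definitions as the basis of the recorded grade.
2. Change the a-d sentence so that meeting at least one criterion makes an AE at least possibly related, in place of definitely or probably related. The two higher grades then need the clear or likely association that the scale asks for.
3. State that related, for expedited reporting, means possibly related or higher. This agrees with the unanticipated-problem definition.
4. Tabulate AEs by arm regardless of attribution, with any related-AE table shown beside it.

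The same 11 coherent patterns still count as related for expedited reporting, so nothing that the a-d rule now captures is lost. A stricter ladder that made plausible timing a condition for every grade above unlikely would not have this property. An event meeting b, c and d but not a would drop out, although the present rule captures it.

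The cost is a small edit to Section 10.4 and to the CRF instructions. The downside is that expedited reporting stays broad: an event with plausible timing and a probable other cause still counts as at least possibly related.
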